## Comparison Group Selection

Each subject will serve as their own control.

## Comments

A 5% increase in subscales are considered meaningful. With a 5% increase with a standard deviation of 0.1 and alpha = 0.007 (to account for multiple tests) power at N = 20 ranges from a low of 0.84 to a high of 0.99 calculated using SAS proc power.

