## **Objectives**

1. Adapt the Living Well in the Community peer led health promotion program to address the needs of families caring for adolescents living with a disability in rural, southeast Georgia.
2. Implement the adapted Living Well in the Community program in southeast Georgia.
3. Evaluate the adapted Living Well in the Community program.

Investigators will provide technical assistance to local Peer Facilitators and develop a Parent Facilitator Guide to accompany the Living Well in the Community program. A local community partner will recruit 20 families to participate in the pilot of the adapted program. Four members of the Navigator Team will serve as Parent Mentors and lead 5 families through adapted Living Well in the Community program. Investigators will 1) matching parent facilitators with families, 2) scheduling and confirming weekly meetings, 3) scheduling and confirming bi-weekly workshops and 4) leading bi-weekly workshops that will include extended programming for parents and children.

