## Instrumentation

**Quantitative.** The Patient Reported Outcomes Measurement Information System (PROMIS; see attached) will be used to examine mental health and physical activity. PROMIS has 4 unique features: comparability, reliability/validity, flexibility, and inclusiveness. Its measures have been standardized, allowing comparisons across subpopulations and with the general population. Recently, pediatric versions have been adapted for proxy reporting in the areas of mental, physical, and social health.

**Qualitative.** The project directors will conduct face to face interviews with the children living with disability participants and focus groups with the parent/caregiver participants to explore program effects and collect feedback on the adapted program. The project directors will aim to recruit 8-10 participants for the face-to-face interviews and 8-10 focus group participants from the families who participated in the curriculum. Both interviews and focus groups will last approximately 60 minutes. Interview and focus group guides will be developed and used to guide each interview and focus group. Interviews and focus groups will be recorded. Audio recordings will be transcribed verbatim. Transcripts will be analyzed using content analysis to identify codes and emergent themes.

The evaluation team will collect questionnaires pre and post implementation. Each facilitator will have an envelope to return to the evaluation team. The evaluation team will enter the data into a SPSS database and analyze the results. A Multivariate analysis of variance (MANOVA) will be conducted for each survey with appropriate post hoc tests. Interview and focus group guides will be developed and used to guide each interview and focus group. Interviews and focus groups will be recorded. Audio recordings will be transcribed verbatim. Transcripts will be analyzed using content analysis to identify codes and emergent themes.

Only data will only be presented in aggregate post analysis.

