## Statistical Analysis Overview

The evaluation team will collect questionnaires pre and post implementation. Each facilitator will have an envelope to return to the evaluation team. The evaluation team will enter the data into SAS database and analyze the results. We will evaluate differences between pre and post measures using a paired t-test for normally distributed data and Friedman's test for non-normally distributed scales.

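### The stated power of 0.84 to 0.99 does not follow from the single effect, SD, alpha and N given; it needs a mean change of 0.91 to 1.25 SDs of change

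*Combined protocol and SAP*

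**What the plan says.** The plan's only power statement is in the Comments section that follows Comparison Group Selection. It first defines the target: "A 5% increase in subscales are considered meaningful". It then gives the inputs, "With a 5% increase with a standard deviation of 0.1 and alpha = 0.007 (to account for multiple tests) power at N = 20", and the result, which "ranges from a low of 0.84 to a high of 0.99 calculated using SAS proc power".

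The test is identified elsewhere in the same document. Statistical Analysis Overview compares pre and post measures "using a paired t-test for normally distributed data", with Friedman's test for non-normal scales. Comparison Group Selection states: "Each subject will serve as their own control". The Method section makes the t-test two-sided.

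On the measurement scale, Instrumentation says of PROMIS: "Its measures have been standardized, allowing comparisons across subpopulations and with the general population". The text gives no score range, baseline mean, SD or pre-post correlation for any subscale.

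**The concern.** A paired t-test has a single power once the mean change, the SD of change, alpha and the number of pairs are fixed. The plan fixes what look like all four and still reports a range, so at least one input varied without being stated. It is also unclear whether the 5% is an absolute change or relative to a baseline mean, and whether 0.1 is the SD of scores at one occasion or of the paired change.

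This matters for reading the results. The sentence ties the claimed power to the change the plan calls meaningful, so a reader would take a null result as fair evidence against a 5% improvement. That inference is reasonable if power is 0.99 and weak if it is 0.25. The sample size itself does not appear to rest on this sentence: Objectives plans 20 families and says "Four members of the Navigator Team will serve as Parent Mentors and lead 5 families" each, which makes 20. Only the power claim is at stake.

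**Working it through.** **Inputs from the documents.** 20 pairs, alpha 0.007, a 5% increase, SD 0.1 (power statement in Comments); paired comparison (Statistical Analysis Overview; Comparison Group Selection); two-sided (Method). The alpha is close to 0.05/7 = 0.00714.

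**Formula.** Let d = mean change / SD of change. The test statistic has a noncentral t distribution with 19 degrees of freedom and noncentrality d × √20. The two-sided critical value at alpha 0.007 is 3.023. Power is the probability that the statistic falls outside ±3.023.

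**Step 1: try to reproduce the plan's figure.** Read 5% as 0.05 and 0.1 as the SD of change:

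- d = 0.05 / 0.1 = 0.5; noncentrality = 0.5 × 4.472 = 2.236; power = 0.251.

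The 0.84 to 0.99 range is not reproduced. Nor is it by changing one other feature at d = 0.5:

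| Variant at d = 0.5 | Power |
|---|---|
| alpha 0.05/7, two-sided | 0.254 |
| alpha 0.007, one-sided | 0.346 |
| alpha 0.05, two-sided | 0.565 |
| alpha 0.05, one-sided | 0.695 |
| 40 pairs, alpha 0.007, two-sided | 0.625 |
| two independent groups of 20, alpha 0.007 | 0.132 |

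**Step 2: solve for the d that the stated power requires** (two-sided alpha 0.007, 20 pairs).

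| Power | d needed |
|---|---|
| 0.50 | 0.667 |
| 0.80 | 0.876 |
| 0.84 | 0.914 |
| 0.90 | 0.986 |
| 0.99 | 1.248 |

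The ratio between the ends of the stated range is 1.248 / 0.914 = 1.37. Rounding does not remove it: a power printed as 0.84 (0.835 to 0.845) needs d of 0.909 to 0.920, and one printed as 0.99 (0.985 to 0.995) needs 1.209 to 1.311. The spread is therefore at least 1.209 / 0.920 = 1.31 and at most 1.311 / 0.909 = 1.44. Using alpha 0.05/7 gives 0.912 and 1.246, so rounding of alpha does not matter either. Simulation with 200,000 data sets of 20 pairs agrees: power 0.253 at d = 0.5, 0.840 at 0.914 and 0.990 at 1.248.

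**Step 3: ask which unreported inputs would give the range.** The correlations and baseline means below are assumptions, since the documents give none.

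*Absolute change of 0.05, with 0.1 as the SD of scores at one occasion.* SD of change = 0.1 × √(2(1 − ρ)), where ρ is the pre-post correlation.

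| ρ | SD of change | d | Power |
|---|---|---|---|
| 0 | 0.141 | 0.354 | 0.10 |
| 0.5 | 0.100 | 0.500 | 0.25 |
| 0.7 | 0.077 | 0.645 | 0.47 |
| 0.8 | 0.063 | 0.791 | 0.69 |
| 0.85 | 0.055 | 0.913 | 0.84 |
| 0.92 | 0.040 | 1.250 | 0.99 |

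*Relative 5%, with 0.1 as the SD of scores.* Baseline mean needed = d × SD of change / 0.05.

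| ρ | Mean for power 0.84 | Mean for power 0.99 |
|---|---|---|
| 0 | 2.59 | 3.53 |
| 0.5 | 1.83 | 2.50 |
| 0.7 | 1.42 | 1.93 |
| 0.85 | 1.00 | 1.37 |

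The ρ = 0.5 row is the same as taking 0.1 to be the SD of change itself. So the range is attainable, but each route needs figures that the plan does not state.

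**The case against.** The strongest reply is that this is incomplete reporting rather than an arithmetic error. The statement speaks of subscales in the plural, and a percentage increase is naturally relative, so the absolute change would differ with each subscale's mean and a range of power is what one would expect. Step 3 shows that admissible inputs do give 0.84 to 0.99. The PROMIS attachment mentioned under Instrumentation is also not in the file, and it may show the score scale.

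Much of this stands. The sponsor may have run a correct calculation with subscale means, and nothing here shows otherwise. But that explanation depends on the very figures the sentence leaves out, and an attached questionnaire could show a score range but is unlikely to supply this study's assumed means or correlations. As printed, the result does not come from the inputs beside it.

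Two further points are fair. The powers from 0.10 to 0.99 in Step 3 reflect the cases chosen and are not bounds on the true power; likewise 0.25 is one reading, not the trial's actual power. And this is a small mixed-methods pilot in which no estimate, test or p-value would change. That limits the consequence to how the power claim, and any null result, is interpreted.

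**Conclusion.** The concern holds. With 20 complete pairs and two-sided alpha 0.007, the stated power requires a mean change of 0.91 to 1.25 SDs of change, and the plan gives neither that ratio nor the inputs that would produce it. The direct reading of the printed inputs gives 0.25. The conclusion on the required ratio rests only on the paired two-sided t-test, alpha and N in the plan; the correlations and baseline means shown are back-solved assumptions. The calculation allows for no dropout and does not cover scales sent to Friedman's test. It should be fixed, because this is the plan's only statement of what the study can detect, but it does not undermine the design.

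**What to change.** Recompute and restate the power sentence with every input shown, for example:

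> Power is for a two-sided paired t-test, alpha 0.007, 20 complete pairs. The 5% increase is [absolute, 0.05 / relative to baseline means of __ to __]. The value 0.1 is the SD of [paired change / scores, with an assumed pre-post correlation of __]. Across subscales, [input] varies from __ to __, giving power of __ to __.

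If those inputs cannot be supported, delete the 0.84 to 0.99 range and use a scale-free statement:

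> With 20 complete pairs and two-sided alpha 0.007, power is 0.25 for a standardised change (mean change divided by SD of change) of 0.5, 0.80 for 0.88, 0.84 for 0.91 and 0.99 for 1.25.

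The first option is better, because only it says whether the 5% change is detectable. If the second is used, the plan should add that power for a 5% change cannot be given without the subscale means and SDs of change.

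The cost is one reworded sentence, from inputs the sponsor should hold from its own calculation. The power shown may turn out less favourable. Sample size, test and data collection are unaffected.

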## Type of Statistical Test

Superiority

## **Statistical Test of Hypothesis**

Null: There is no differences in scale and subscale measures between pre and post outcome measures.

Alternative: There are differences in scale and subscale measures between pre and post outcome measures.

All data will be analyzed by paired t-tests/Friedman's test. To accommodate multiple comparisons, all p-values will be adjusted using Hochberg's adjustment.

### **P-Value**

p = .05

### **Comments**

Hochberg's adjustment

### **Method**

t-Test, 2-Sided

Other

### **Other Method Name**

Friedman's test

### **Estimation Parameter**

Mean Difference (Final Values)

Median Difference (Final Values)

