### **Parameter Dispersion Type**

Standard Error of the Mean

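### The plan names the standard error of the mean as its only dispersion measure although it also plans to report a median, and the label for that median does not fix it as a within-person change

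*Combined protocol and SAP*

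**What the plan says.** - *Comparison Group Selection*: "Each subject will serve as their own control". There is one group and no parallel comparator.
- *Statistical Analysis Overview*: "We will evaluate differences between pre and post measures using a paired t-test for normally distributed data", and "Friedman's test for non-normally distributed scales".
- *Statistical Test of Hypothesis*: the null is "There is no differences in scale and subscale measures between pre and post outcome measures".
- *Estimation Parameter*: two entries, "Mean Difference (Final Values" and "Median Difference (Final Values".
- *Parameter Dispersion Type*: one entry, "Standard Error of the Mean".

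No section says whether the median is the median of the paired changes or the difference between the post median and the pre median. None says which data supply the SEM. No interquartile range or confidence interval is planned for any estimate.

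**The concern.** Both planned tests compare each person with themselves, so the matching estimate is a within-person change. The reporting fields depart from that in two ways.

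First, the median is reported only where a scale has been judged non-normal, yet the one dispersion measure on offer describes a mean. Anyone who follows the plan attaches an error bar to each median result that does not belong to it.

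Second, a final-values label suits a comparison of end-of-study scores between groups. In a single-group pre-post design it leaves the median result undefined.

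This is a 20-family pilot without a control group, so the estimates and their precision are a large part of what it can deliver. The plan also sets a benchmark for change ("A 5% increase in subscales are considered meaningful"), and readers can judge results against it only if each estimate of change carries a valid measure of uncertainty.

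**Working it through.** The plan gives no figure on this point to reproduce. Its only computed figure is the power range in *Comments*, which does not bear on it. The inputs from the plan are n = 20, two time points, paired data, Friedman's test for non-normal scales, and the SEM as sole dispersion measure. The shape of the score changes is not given, so every distribution below is an assumption.

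**1. What Friedman's test addresses at two time points.** With k = 2, Friedman's statistic is 12/[nk(k+1)] × ΣR² − 3n(k+1), where R is the rank sum at each time point. Take n = 20 with 13 people rising and 7 falling. The rank sums are 13×1 + 7×2 = 27 (pre) and 13×2 + 7×1 = 33 (post). The statistic is 12/120 × (729 + 1089) − 180 = 181.8 − 180 = 1.8. The sign-test statistic is (2×13 − 20)²/20 = 36/20 = 1.8. They are the same test, so the matching estimate is the median of the paired changes.

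**2. SEM against the true standard error of the median change.** The SEM is SD/√n, with the SD taken from the paired changes. Simulated samples of 20 changes gave:

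| Assumed shape of changes | Mean SEM | True SE of median | Ratio |
|---|---|---|---|
| Normal, SD 1 | 0.220 | 0.271 | 0.81 |
| Exponential | 0.215 | 0.220 | 0.98 |
| Lognormal, sigma 1 | 0.415 | 0.287 | 1.45 |

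The SEM is about 19% too short in the first case, nearly right in the second and about 45% too long in the third. A reader who does not know the shape cannot correct for it.

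**3. Difference of medians against median of changes.** With a normal baseline (SD 0.1) and lognormal changes (sigma 1, scaled to SD 0.1), the median change was 0.046 and the difference of medians 0.064. With a skewed (gamma, shape 1) baseline scaled to SD 1.8, and normal changes with mean 0.913 and SD 1, the difference of medians averaged 1.08 against 0.913, an excess of about 19%. With a symmetric baseline and the same changes it averaged 0.914, so the excess vanished. The two quantities can differ, but need not.

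**4. The mean.** With complete pairs, mean(post) − mean(pre) = mean(post − pre) by algebra. The check gave 0.0761 both ways. The point estimate is therefore the one the paired t-test uses, and SD(post − pre)/√n is its correct standard error.

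**5. A dispersion measure that fits the median change.** Inverting the sign test at n = 20 gives the interval from the 6th to the 15th ordered change. Its coverage is 1 − 2 × P(Bin(20, 0.5) ≤ 5) = 1 − 2 × 0.0207 = 0.959, whatever the shape of a continuous distribution of changes.

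**The case against.** The strongest reply is that these sections are short form entries, not analysis prose, and that the rest of the plan already fixes the comparison as paired. With no second group, the mean entry can only sensibly be post minus pre, and its SEM would naturally come from the paired test. The median entry may already mean the median of the paired differences. The issue is one of presentation and changes no test, p-value or error rate.

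Most of this stands, and it rules out several stronger readings that a reader might infer:

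- *That the mean result differs from the change being tested.* It does not, given complete pairs.
- *That separate pre and post SEMs will be used, so that the bar ignores the pairing.* With equal variances, combining them would overstate the standard error by 1/√(1−r), for example 1.8 times at r = 0.7. No section says this will be done, and the plan gives no pre-post correlation.
- *That every non-normal scale will have an estimate that does not match its test.* This follows only if a difference of two medians is meant, which the plan does not say.
- *That the bar on the median is too short by a fixed percentage.* The direction reverses with the assumed shape.

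What the reply does not remove is the single dispersion measure. Under either reading of the median entry, an SEM is not its standard error, and no other section supplies an alternative.

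**Conclusion.** The point holds for the median result. As written, the plan attaches the wrong kind of error bar to it. The size depends on the unknown shape of the changes: from about 19% too short to about 45% too long at n = 20 across the three assumed distributions, and close to right in one of them. The final-values label is a separate ambiguity that could, but need not, produce an estimate different from the median change that Friedman's test addresses.

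For the mean result the plan needs clarification, not correction: its SEM is right provided the pairs are complete and it is computed from the paired differences.

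The consequence is confined to reporting. It should be corrected, but it does not threaten the validity of the tests.

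**What to change.** - *Estimation Parameter*: replace the two entries with the mean within-person change and the median within-person change, both defined as post minus pre in participants with both measurements.
- *Parameter Dispersion Type*: for the mean change, give the standard error or 95% CI computed from the paired differences. For the median change, give the distribution-free CI from inverting the sign test (the 6th and 15th ordered changes if all 20 pairs are complete, about 96% coverage). Do not attach an SEM to a median.
- Keep estimate and test matched. The sign-test interval goes with Friedman's test at two time points. A Hodges-Lehmann estimate with a signed-rank interval should be used only if the planned test is changed to the signed-rank test, because the two targets can differ (for exponential changes the median is 0.69 and the Hodges-Lehmann target 0.84).

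The cost is a change of wording in two sections and a few lines of code. No new data are needed, and the planned tests stay as they are.

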### **Parameter Dispersion Type**

Standard Error of the Mean
